7.2 Rationale for Study Design

In this study, the on-eye performance of the investigational AOHG toric lens and the commercially available AO toric lens will be assessed in a prospective, double-masked, bilateral crossover design with approximately 30 minutes of exposure to each study lens. The study design as well as the exposure duration of study lenses is supported by the nonclinical and clinical data presented in the IB.

7.3 Rationale for Duration of Treatment/Follow-Up

The duration of exposure to the investigational products was chosen to address the objective of this study, and is aligned with AO toric fitting guidelines for initial fit assessment following lens insertion.

7.4 Rationale for Choice of Control Product

AO toric lenses were chosen as the control product to address the study objectives. Both AOHG toric and AO toric lenses are fluoro-silicone hydrogel lenses consisting of 33% water and 67% lotrafilcon B, and are prescribed for monthly wear. AO toric lenses are indicated for the optical correction of astigmatism of up to 6D or less in people with healthy eyes with or without refractive ametropia (myopia or hyperopia).

Document: TDOC-0054499 Version: 1.0; CURRENT; Most-Recent; Effective

Status: Effective Page 24 of 54

7.5 Data Monitoring Committee

Not applicable

8 STUDY POPULATION

The study population consists of adult male and female subjects (aged 18 and over) with non-diseased eyes, who require optical correction for astigmatism. It is aimed to enroll approximately 35 subjects in 1 US site, with a potential 2nd US site being added if necessary to meet target enrollment. Site-specific targets may vary based upon individual site capabilities. Estimated time needed to recruit subjects for the study is approximately 4 weeks.

The intended study population consists of volunteer subjects aged 18 or over who are adapted soft contact lens wearers, have at least 3 months of contact lens wearing experience, and who wear their habitual lenses at least 3 days per week and at least 8 hours per day.

Subjects must require contact lens sphere power from -0.50 to -8.00 D; cylinder power less than or equal to -2.25 DC; and for cylinder powers greater than -1.00 DC, axis should be between 60° to 120° or 30° to 150° inclusive. Because an approximately 10% screening failure rate is expected, approximately 35 subjects are expected to be enrolled to obtain a target of 30 completed subjects.

8.1 Inclusion Criteria

Written informed consent must be obtained before any study specific assessment is performed. Upon signing informed consent, the subject is considered enrolled in the study.

Subjects eligible for inclusion in this study must fulfill **all** of the following criteria:

1.	Subject must be at least 18 years of age and must be able to understand and sign an IRB/IEC approved Informed Consent form.
2.	Willing and able to attend the single study visit as required per protocol.
3.	Successful wear of soft contact lenses for vision correction in both eyes during the past 3 months for a minimum of 3 days per week and 8 hours per day.
4.	Subjects must have ≥ 0.75 D corneal or manifest astigmatism.

Document: TDOC-0054499 Version: 1.0; CURRENT; Most-Recent; Effective

Status: Effective Page 25 of 54

5.	Requiring contact lens sphere power from -0.50 to -8.00 D; cylinder power less than or
	equal to -2.25 DC; and for cylinder powers greater than -1.00 DC, axis should be within
	± 30 ° from 90° or 180° axis (i.e., between 60° to 120° or 30° to 150° inclusive).
6.	Distortion-free keratometric readings at baseline.
7.	Best spectacle corrected visual acuity 20/25 or better in each eye.

8.2 Exclusion Criteria

Subjects fulfilling any of the following criteria are not eligible for participation in this study.

1.	Any anterior segment infection, inflammation, or abnormality or disease (including
	systemic) that contraindicates contact lens wear, as determined by the Investigator.
2.	Any use of systemic or ocular medications for which contact lens wear could be
	contraindicated, as determined by the investigator.
3.	History of ocular or intraocular surgery, including refractive surgery which contact
	lens wear could be contraindicated, as determined by the Investigator and/or irregular cornea.
4.	Biomicroscopy findings at baseline that are moderate (Grade 3) or higher and/or
	corneal vascularization that is mild (Grade 2) or higher; presence of corneal
	infiltrates
5.	Current or history of pathologically dry eye in either eye that, in the opinion of the
	Investigator, would preclude contact lens wear.
6.	Current or history of herpetic keratitis in either eye.
7.	Eye injury within 12 weeks immediately prior to enrolling in this trial.
8.	History of intolerance or hypersensitivity to any component of the study lenses.
9.	Any clinically significant corneal thinning disorder such as keratoglobus,
	keratoconus or pellucid marginal degeneration
10.	Enrollment of site staff or family/household members of the site staff who are listed
	on the study personnel log as having a role in the execution of this study.
11.	Participation of the subject in a clinical trial within the previous 30 days or currently
	enrolled in any clinical trial.

Document: TDOC-0054499 Version: 1.0; CURRENT; Most-Recent; Effective

Status: Effective Page 26 of 54

8.3 Rescreening of Subjects

Rescreening of subjects is not allowed in this study.

9 TREATMENTS ADMINISTERED

9.1 Investigational Product(s)

Test Product(s): AIR OPTIX plus HYDRAGLYDE for Astigmatism

soft contact lenses

Control Product(s): AIR OPTIX for Astigmatism soft contact lenses

Table 9–1 Test Product

Test Product	AIR OPTIX plus HYDRAGLYDE for Astigmatism soft contact
	lenses (AOHG toric) - LID009941
2.5	
Manufacturer	Alcon Laboratories, Inc.
	[name]
	USA
Indication for use and intended purpose in the	The intended use of this contact lens is for vision correction. Limited parameters are available for use in this non-dispensing study in accordance with the study objective.
current study	study in decordance with the study objective.
Product description	Material: lotrafilcon B
and parameters	Water content: 33%
available for this	Power range:
study	o Sphere: -1.00 D, -3.00 D and -5.00 D
	o Cylinder: -1.25 DC
	o Axis availability: 90 & 180
	Base curve (mm): 8.7 mm (target)
	Diameter (mm): 14.5 mm (target)
	Other: Additional details can be found in the IB
Formulation	Silicone Hydrogel. Additional details can be found in the IB for
	AOHG toric.

Document: TDOC-0054499 Version: 1.0; CURRENT; Most-Recent; Effective

Status: Effective Page 27 of 54

Number/Amount of product to be provided to the subject	 Wear: Daily Wear for this study Bilateral Replacement period: N/A for this non-dispense study Exposure: Approximately 30 minutes Lens Care: N/A Additional details can be found in the MOP One pair of test study lenses will be provided to the subject at a single visit to be worn for in-office use only. The test lenses will be removed after approximately 30 minutes of lens wear. The test lenses will not be dispensed to subject to take home. Replacement lenses are allowed only if there is a device deficiency (eg, torn lens).
	(eg, torn tens).
Packaging description	Blister containing phosphate buffered saline solution with wetting agents
Labeling description	 Lens Foil label includes: material name and identifier base curve diameter manufacturing protocol number packing solution power lot number expiration date content statement investigational device statement Sponsor information Provided in boxes of 40 lenses per power per box, identified with the following: a color coded label stating the protocol number material identifier power an investigational use only statement tracking number

Document: TDOC-0054499 Version: 1.0; CURRENT; Most-Recent; Effective

Status: Effective Page 28 of 54

Storage conditions	Stored at room temperature.
Additional information	N/A
Supply	Refer to the MOP for a detailed description

Table 9–2 Control Product

Control Product(s)	AIR OPTIX for Astigmatism soft contact lenses (AO toric)				
Manufacturer	Alcon Laboratories, Inc.				
	[name]				
	USA				
Indication for Use	The intended use of this contact lens is for vision correction.				
	Limited parameters are available for use in this non-dispensing				
	study in accordance with the study objective.				
Product description	Material: lotrafilcon B				
and parameters	Water content: 33%				
available for this	Power range:				
study	o Sphere: -1.00 D, -3.00 D and -5.00 D				
	o Cylinder: -1.25 DC				
	o Axis availability: 90 & 180				
	Base curve (mm): 8.7 mm (target)				
	Diameter (mm): 14.5 mm (target)				
	Other: Additional details can be found in the IB				
Formulation	Silicone Hydrogel. Additional details can be found in the IB for AO				
	toric.				
Usage	Wear:				
	Daily Wear for this study				
	Bilateral				
	Replacement period: N/A for this non-dispense study				

Document: TDOC-0054499 Version: 1.0; CURRENT; Most-Recent; Effective

Status: Effective Page 29 of 54

Status. Effective	1 age 25 01 34		
	Exposure: Approximately 30 minutes		
	• Lens Care: N/A		
	Additional details can be found in the MOP		
Number/Amount of	One pair of control study lenses will be provided to the subject at a		
Product to be	single visit to be worn for in-office use only. The control lenses will		
Provided to the	be removed after approximately 30 minutes of lens wear.		
subject			
	The control lenses will not be dispensed to subject to take home.		
	Replacement lenses are allowed only if there is a device deficiency		
	(eg, torn lens).		
Packaging	Blister containing phosphate buffered saline solution with wetting		
description	agents		
Labeling description	Lens Foil label includes:		
	- material name and identifier		
	- base curve		
	- diameter		
	- packing solution		
	- power		
	- lot number		
	- expiration date		
	- content statement		
	- Sponsor information		
	Provided in boxes of 6 lenses per power per box, identified with		
	the following:		
	- a color coded label stating the protocol number		
	- material identifier		
	- power		
	- an investigational use only statement		
	- tracking number		
Storage conditions	Stored at room temperature.		
Additional	N/A		
identifying			
information			
Supply	Refer to the MOP for a detailed description.		

Document: TDOC-0054499 Version: 1.0; CURRENT; Most-Recent; Effective

Status: Effective Page 30 of 54

9.2 Other Medical Device or Medication Specified for Use During the Study

No other medical devices or medications are required to be used in conjunction with the investigational products during the clinical study.

9.3 Treatment Assignment / Randomization

Subjects will be randomized in a 1:1 ratio to receive treatment in crossover sequence AOHG toric then AO toric or AO toric then AOHG toric, respectively.

Only after signing the ICF, a subject will be assigned a subject number by the electronic data capture system.

A randomization list will be generated using a validated system that automates the random assignment of treatment arms to randomization numbers in the specified ratio. Subjects will be assigned treatment according to the randomization list uploaded in the iMedidata BALANCE system. The randomization list will be generated and maintained by the Study Sponsor.

At Visit 1, all eligible subjects will be randomized via the EDC/IRT integration system to one of the lens sequences. The Investigator or delegate will access the respective system after confirming that the subject meets all the eligibility criteria. A randomization number will be automatically assigned to the subject according to the subject randomization list but will not be communicated to the site user. The EDC/IRT integration system will inform the site user of the treatment assignment to be dispensed to the subject.

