9.4 Treatment masking

This study is double-masked, with subjects randomized to use AOHG toric and AO toric lenses (in a crossover fashion) for the duration of the approximately 30 minute treatment period for each lens pair. All study team members (at the site and the Study Sponsor) are masked to the assigned sequence with the exception of those mentioned in Table 9-3.

Table 9–3 Unmasked Individuals Associated with the Study

Unmasked Individual	Extent of Unmasking	Rationale
Unmasked Study	The Unmasked Study	The Unmasked Study
Coordinator(s)	Coordinator(s) will manage IP	Coordinator(s) will be
	inventory, as well as IP	unmasked to allow for
	administration. This individual	processing of IP shipment,
	will have access to IP supply,	storage, and dispensing, as

Document: TDOC-0054499 Version: 1.0; CURRENT; Most-Recent; Effective

Status: Effective Page 31 of 54

Unmasked Individual	Extent of Unmasking	Rationale
	accountability logs, and other	well as accountability for all
	documents or supplies	IP.
	pertaining to IP. The unmasked	
	coordinator will also assist with	
	device deficiency and adverse	
	event reporting.	
LCSM	The LCSM will have access to	The LCSM will be
	IP supply, accountability logs,	unmasked to allow for
	and other documents or	oversight of the CSM, in
	supplies pertaining to IP. This	conjunction with all IP
	individual assists with masked	accountability tasks.
	and unmasked data reviews.	
CSM	CSM will have access to IP	The CSM will be unmasked
	supply, accountability logs, and	to allow for performance of
	other documents or supplies	IP accountability,
	pertaining to IP accountability.	management of device
	This individual monitors	deficiencies and related AE
	unmasked and masked study	lens returns, and any other
	data.	IP related tasks.
Unmasked Data	The Unmasked Data	The Unmasked Data
Manager(s)	Manager(s) will have access to	Manager(s) will be
	restricted fields in RAVE that	unmasked to allow for
	would contain unmasking data.	review of all restricted data.
IRT Manager	The IRT manager will be	The IRT manager is
	unmasked to allow for system	unmasked to all aspects of
	programming, testing, and to	the trial for system
	allow for technical oversight of	development purposes.
	the system.	
Randomization Specialist	The Randomization Specialist	Generates and therefore has
	will be unmasked to allow for	full knowledge of treatment
	generation of the randomization	codes but otherwise is

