	list and uploading of that list	operationally not associated
	into the IRT system.	with the CTT or any
		decision making aspects
		related to clinical trial
		design, execution, or
		reporting.

Document: TDOC-0054499 Version: 1.0; CURRENT; Most-Recent; Effective

Status: Effective Page 32 of 54

This level of masking will be maintained throughout the conduct of the study. Unmasking will occur only after all planned study data have been validated, and the database locked.

Masked study personnel must avoid seeking information that may compromise masking. Unmasked study personnel must not disseminate information that is potentially unmasking to any masked personnel. The masked and unmasked site personnel must coordinate all study activities as necessary to protect masking and minimize bias during the study.

In the event of a medical emergency where the knowledge of subject treatment is required, an individual Investigator will have the ability to unmask the treatment assignment for a specific subject after contacting an appropriate Study Sponsor representative if time allows.

Unmasking must be done according to the instructions provided for the study IRT system.

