9.5 Accountability Procedures

Upon receipt of the IPs, the Investigator or delegate must conduct an inventory. During the study, unmasked designated study staff must provide the IPs to the subjects in accordance with their randomization assignment. Throughout the study, the Investigator or delegate must maintain records of IP dispensation and collection for each subject. This record must be made available to the study monitor for the purposes of verifying the accounting of IP supplies. Any discrepancies and/or deficiencies between the observed disposition and the written account must be recorded along with an explanation. All IPs sent to the Investigator must be accounted for by Study Sponsor personnel, and in no case be used in an unauthorized situation.

It is the Investigator's responsibility to ensure that:

- All study products are accounted for and not used in any unauthorized manner
- All used foils and unused supplies are retained by designated unmasked staff
- All unused products are available for return to the Study Sponsor, as directed
- Any study lenses associated with a device deficiency or with any product-related
 adverse event (ie, ADE or SADE) are returned to the Study Sponsor for investigation,
 unless otherwise directed by the Sponsor. Refer to Section 11 of this protocol for
 additional information on the reporting of device deficiencies and AEs and the return
 of study products associated with these events.

The Investigator is responsible for proper disposition of all unused IPs at the conclusion of the study, according to the instructions provided in the MOP.

Print Date:

Document: TDOC-0054499 Version: 1.0; CURRENT; Most-Recent; Effective

Status: Effective Page 33 of 54

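### Do protocol sections 9.3 and 9.5 give the masked Investigator the lens assignment?

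*Protocol*

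**What the plan says.** Section 9.3 describes the randomization step at the visit: "The Investigator or delegate will access the respective system after confirming that the subject meets all the eligibility criteria". The randomization number is withheld from the site, but the assignment is not: "The EDC/IRT integration system will inform the site user of the treatment assignment to be dispensed to the subject".

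Section 9.4 states the masking rule. All team members, at the site and at the sponsor, "are masked to the assigned sequence with the exception of those mentioned in Table 9-3". The only site role in that table is the Unmasked Study Coordinator, who handles lens inventory and administration and has access to the accountability logs. The Investigator is not listed. In a medical emergency, "an individual Investigator will have the ability to unmask the treatment assignment for a specific subject".

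Section 9.5 covers accountability. On receipt: "Upon receipt of the IPs, the Investigator or delegate must conduct an inventory". During the study: "Throughout the study, the Investigator or delegate must maintain records of IP dispensation and collection for each subject". The same section says that "unmasked designated study staff must provide the IPs to the subjects in accordance with their randomization assignment", and that unmasked staff retain used foils and unused supplies.

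Section 10.2 leaves the choice of assessor to the Investigator's delegation and the detail of assessments to the manual of procedures. SAP 1.4 says only that the study is double-masked.

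**The concern.** The Investigator's masked status follows from omission from Table 9-3. The emergency route in 9.4 and 11.5 supports it, since it would be pointless for someone already unmasked. Yet 9.3 and 9.5 name that same role for opening the system that displays the assignment and for keeping records that show each subject's lens order. An Investigator who did these tasks in person would no longer be masked.

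The primary endpoint is an axis reading made at the site, classed as Yes between 60° and 120° inclusive, with the AOHG percentage compared numerically with 90%. The protocol does not name the reader or state that the reader is masked, whereas 13.4 does say that the optional sponsor observer stays masked until database lock. If the reader knew which lens was on the eye, a reading near a cut-point could be nudged across it.

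**Working it through.** The plan gives no figure on this point, so the check is whether all the sections can be followed together.

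**Step 1: the tasks side by side.**

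| Task | Section naming the role | Role named | Reveals a subject's sequence? | Within the coordinator's Table 9-3 role? |
|---|---|---|---|---|
| Randomization transaction and assignment display | 9.3 | Investigator or delegate | Yes | Yes, as part of administration and dispensing |
| Inventory on receipt | 9.5 | Investigator or delegate | No, it counts delivered stock | Yes |
| Per-subject dispensing and collection records | 9.5 | Investigator or delegate | Yes | Yes, as part of accountability |
| Handing lenses to subjects | 9.5 | Unmasked staff | Yes | Yes |
| Keeping foils and unused supplies | 9.5 | Unmasked staff | Possibly | Yes |

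That the site user in 9.3 is the Investigator or delegate is an inference from adjacent sentences, but a fair one.

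**Step 2: who can do the two revealing tasks whose role is left open?** There are three possibilities.

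- The Investigator in person: meets 9.3 and 9.5, breaches 9.4.
- A masked delegate: meets 9.3 and 9.5, breaches 9.4.
- The Unmasked Study Coordinator as delegate: meets 9.3, 9.5 and 9.4.

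The third choice satisfies everything, so the sections do not contradict each other. It is also the only choice that does, so the protocol read as a whole already points to it.

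**Step 3: do other rules point the same way?** They do. Section 9.4 says "Masked study personnel must avoid seeking information that may compromise masking". It also forbids unmasked staff to pass on unmasking information and requires masked and unmasked site staff to arrange their work so that masking is protected. Section 11.5 bars disclosure of the device's identity during the study. Table 9-3 refers to restricted fields in the data capture system for unmasking data. It does not expressly cover the randomization display, but it shows that restricted access is part of the set-up.

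**Step 4: scale.** With 30 completers and both eyes counted, there are 30 × 2 = 60 AOHG lenses, and one reading is 1/60 = 1.7 percentage points. The threshold is 0.90 × 60 = 54 Yes readings; 53/60 = 88.3%. If all of about 35 enrolled subjects were fitted, there would be 70 lenses, one reading would be 1/70 = 1.4 points, and 63 Yes readings would be needed. That case assumes no screen failures, against the roughly 10% expected in section 8. These figures give the step size of the percentage under any cause of error. They do not estimate bias from unmasking.

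**The case for a change.** The strongest counter-argument is that nothing obliges the site to choose the coordinator. Section 9.5 shows that its drafters could restrict a task to unmasked staff when they wished: they did so for handing over lenses and for keeping foils, and not for inventory or records. A rule against seeking information does not help someone to whom the system delivers it. Someone who has done the inventory might also recognise stock later: Tables 9-1 and 9-2 give boxes of 40 test lenses and 6 control lenses, and only the test foil lists an investigational device statement. Nor does any sentence bar the coordinator from reading the axis.

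Part of this stands. The wording of 9.3 and 9.5 is looser than that of 9.4, and adding the word unmasked in two places would be tidier. But 9.4 is the section that decides who may know the sequence, and open wording elsewhere gives no exemption from it. The inventory point needs a further step, a masked person seeing a box or foil at the visit, and 9.5 puts both the supply of lenses and the keeping of foils with unmasked staff. A coordinator who read the axis would defeat the double masking and the duty in 9.4 to organise work so as to limit bias. That the reader is unnamed is missing detail: 10.2 sends assessment detail to the manual of procedures, which is not available here, so silence in the protocol does not show that the reader is undefined. Section 13.4 does not settle it either. It has the Investigator and the sponsor observer record separately, and describes the observer's notes as concerning lens fit and surface characteristics.

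**Conclusion.** No change to the plan is needed. The quoted sentences are loosely worded, but they are compatible with 9.4 and Table 9-3, and the one arrangement that satisfies all of them uses a role the protocol already provides. A site that follows the whole protocol keeps the Investigator masked and produces the same descriptive percentage for comparison with 90%. Rewording would only write down a delegation that is already implied.

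Two of the three tasks left to the Investigator or a delegate bear on masking; the receipt inventory does not. The size of any bias cannot be derived from the documents, and no sample size, interval or hypothesis is affected. The conclusion assumes that the site appoints the coordinator described in Table 9-3, delegates the system access and per-subject records to that person, and has someone else read the axis. The documents neither confirm nor contradict that this was done.
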